6.1.3 Dose Modifications

Not applicable.

6.2 Accountability/Handling/Storage/Preparation

6.2.1 Acquisition and Accountability

All the vaccines (and diluents as needed) will be provided by the DMID repository:

DMID Clinical Materials Services Contract
Fisher BioServices
[name]
[name]
[contact]
[contact]
Email: [contact]

All study products will be shipped to the clinical research site upon request and approval from DMID.

Accountability

The participating site PI is responsible for study product distribution and disposition and has ultimate responsibility for study product accountability. The participating site PI may delegate to the participating site's research pharmacist responsibility for study product accountability. The participating site's research pharmacist will be responsible for maintaining complete records and documentation of study product receipt, accountability, dispensation, storage conditions, and final disposition of the study product(s).

Destruction

After the study treatment period has ended or as appropriate over the course of the study after study product accountability has been performed, disposition of unused and used study product vials should occur as noted:

Unused and used study product vials:

Should be destroyed on-site following applicable site procedures or by the site's selected destruction vendor. Following the site's procedure for the destruction of hazardous material or study product destruction policy/SOP when destroying used and unused items with a second staff member's observation and signed verification (two signatures) that the vials were discarded.

A certificate of destruction or documentation of destruction should be provided to the sponsor and retained in the Pharmacy Binder once completed.

Used syringes may be destroyed in accordance with site-specific SOPs.

6.2.2 Formulation and Appearance

mRNA-1273, mRNA-1273.351, mRNA-1273.617.2 and mRNA-1273.529 are provided as a sterile liquid for injection, white to off-white suspension in appearance.

BNT162b2, BNT162b2 (B.1.351) and BNT162b2 (B.1.1.529 Omicron) and BNT162b2 bivalent (wildtype and Omicron BA.1 or wildtype and Omicron BA.4/BA.5) are provided as a sterile, clear colorless liquid for injection.

CoV2 preS dTM-AS03 [D614], CoV2 preS dTM-AS03 [B.1.351], and CoV2 preS dTM-AS03 [D614 + B.1.351] antigen formulations are provided as a sterile, clear, colorless solution of SARS-CoV-2 prefusion S proteins. The antigen solutions can contain endogenous particles. If present, these light-colored particles are slow sinking and suspended in solution. AS03 adjuvant is a whitish to yellowish homogenous milky liquid emulsion. After mixing, the vaccine is a whitish to yellowish homogeneous milky liquid emulsion.

Diluent: 0.9% NaCl for injection, USP

The USP grade 0.9% NaCl or normal saline for injection is a sterile, nonpyrogenic, isotonic solution; each mL contains NaCl 9 mg. It contains no bacteriostatic agent, antimicrobial agent, preservatives, or added buffer and is supplied only in single-dose containers.

Each of the study products will be labeled according to manufacturer specifications and include the statement "Caution: New Drug Limited by Federal Law to Investigational Use."

6.2.3 Product Storage and Stability

The storage of mRNA-1273, BNT162b2, and CoV2 preS dTM-AS03 vials depend on the presentation (i.e. commercial lots have different storage conditions from investigational lots). For these reasons, refer to the MOP for storage conditions for vaccine candidates as well as storage of diluent.

Prepared doses are stable for clinical in-use for:

- mRNA-1273, mRNA-1273.351, mRNA-1273.617.2 and mRNA-1273.529: up to 8 hours at room temperature
- BNT162b2 bivalent (wildtype and Omicron BA.1 or wildtype and Omicron BA.4/BA.5): up to 12 hours between 2 and 30°C (35 to 86°F) after vial is first punctured.
- BNT162b2, BNT162b2 (B.1.351) and BNT162b2 (B.1.1.529) Omicron BA.1 and BA.4/BA.5: up to 6 hours at room temperature after 1st vial is punctured.
- CoV2 preS dTM-AS03 [D614], CoV2 preS dTM-AS03 [B.1.351], and CoV2 preS dTM-AS03 [D614 + B.1.351]: up to 12 hours post preparation at 2 to 8 °C or at controlled room temperatures (up to 23 to 27 °C) and must be protected from light

Study Product Temperature Accountability

The temperature of the storage unit must be manually recorded daily (excluding non-business days and holidays, as applicable) and continuously monitored and recorded during the course of this trial per site-specific SOPs, and documentation will be maintained. If the temperature fluctuates outside of the required range, the affected study product(s) must be quarantined at the correct storage temperature and labeled as 'Do Not Use' (until further notice).

Study product must be stored in a secure area with limited access (pharmacy staff only) and must be stored as above.

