6. STUDY PRODUCT

6.1 Study Product(s) and Administration

6.1.1 Study Product Description

mRNA-1273 (prototype), mRNA-1273.351 (Beta), mRNA-1273.617.2 (Delta) and mRNA-1273.529 (Omicron)

mRNA-1273 (0.2 mg/mL) is an LNP dispersion containing an mRNA that encodes for the pre fusion stabilized S protein of the Wuhan-Hu-1 strain of SARS-CoV-2. mRNA-1273 consists of an mRNA Drug Substance that is manufactured into LNPs composed of the proprietary ionizable lipid, SM-102, and 3 commercially available lipids, cholesterol, 1,2-distearoyl-sn-glycero-3-phosphocholine (DSPC), and PEG2000 DMG.

mRNA-1273.351 (0.1 mg/mL) is formulated in the same way but contains mRNA that encodes for the pre fusion stabilized S protein of the B.1.351 (Beta) variant SARS-CoV-2 strain.

mRNA-1273.617.2 (0.2 mg/mL) is formulated in the same way but contains mRNA that encodes for the pre fusion stabilized S protein of the B.1.617.2 (Delta) variant SARS-CoV-2 strain.

mRNA-1273.529 (0.2 mg/mL) is formulated in the same way but contains mRNA that encodes for the pre fusion stabilized S protein of the B.1.1.529 (Omicron) variant SARS-CoV-2 strain.

BNT162b2 (wildtype), BNT162b2 (B.1.351, Beta), BNT162b2 (B1.1.529, Omicron), BNT162b2 bivalent (wildtype and Omicron BA.1) and BNT162b2 bivalent (wildtype and Omicron BA.4/BA.5)

BNT162b2 (500 mcg/mL for stage 2) is a preservative-free, sterile dispersion of RNA formulated in LNP in aqueous cryoprotectant buffer. mRNA encodes for the pre fusion stabilized S protein of the ancestral strain of SARS-CoV-2.

BNT162b2 (B.1.351) (500 mcg/mL for stage 2) is formulated in the same way but contains mRNA that encodes for the pre fusion stabilized S protein of the B.1.351 (Beta) variant SARS-CoV-2 strain.

BNT162b2 (B.1.1.529)(500 mcg/mL for stage 2) is formulated in the same way but contains mRNA that encodes for the pre fusion stabilized S protein of the B.1.1.529 (Omicron) variant SARS-CoV-2 strain.

BNT162b2 bivalent (wildtype and Omicron BA.1 100mcg/mL for stage 4) is formulated in the same way but contains mRNA that encodes for the pre fusion stabilized S protein of the Omicron BA.1 variant SARS-CoV-2 strain and the ancestral strain of SARS-CoV-2..

BNT162b2 bivalent (wildtype and Omicron BA.4/BA.5 100mcg/mL for stage 4) is formulated in the same way but contains mRNA that encodes for the pre fusion stabilized S protein of the Omicron BA.4/BA.5 variant SARS-CoV-2 strain and the ancestral strain of SARS-CoV-2.

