6.1.2 Dosing and Administration

mRNA-1273, mRNA-1273.351, mRNA-1273.617.2 and mRNA-1273.529

mRNA-1273 (0.2 mg/mL), mRNA-1273.351 (0.1 mg/mL), mRNA-1273.529 (0.2 mg/mL), and mRNA-1273.617.2 (0.2 mg/mL).

Products will be used alone or in combination as specified in [Table 1](#), and will be diluted in 0.9% NaCl for injection, USP to obtain an antigen content of 50 mcg in a 0.5 mL dose. Each dose will be administered via IM injection into the deltoid muscle.

The expiration time of the dosing syringe containing the prepared study vaccine is 8 hours at room temperature after the solution is drawn into the dosing syringe.

When applicable, the second dose of study vaccine can be administered in either arm regardless of the arm that previously administered.

BNT162b2, BNT162b2 (B.1.351), BNT162b2 (B1.1.529, Omicron), BNT162b2 bivalent (wildtype and Omicron BA.1) and BNT162b2 bivalent (wildtype and Omicron BA.4/BA.5)

BNT162b2, BNT162b2 (B.1.351) and BNT162b2 (B1.1.529 Omicron) at 500 mcg/mL concentration for stage 2 and will be used alone or in combination as specified in [Table 1](#) and will be diluted in 0.9% NaCl for injection, USP to obtain an antigen content of 30 mcg in a 0.3 mL dose. Each dose will be administered via IM injection into the deltoid muscle.

For stage 4, BNT162b2 bivalent (wildtype and Omicron BA.1 or wildtype and BA.4/BA.5) are provided at 100 mcg/mL concentration and neither dilution nor mixing are needed for these formulations.

CoV2 preS dTM-AS03 [D614], CoV2 preS dTM-AS03 [B.1.351], and CoV2 preS dTM-AS03 [D614 + B.1.351]

The multi-dose vial of CoV2 preS dTM antigen, either monovalent or bivalent antigen, will be mixed with the multi-dose vial of AS03 adjuvant prior to administration to obtain an antigen content of 5 mcg in a 0.5 mL dose. Vaccine formulations will be prepared in the CoV2 pres dTM antigen vials by adding an equal volume of adjuvant. A maximum of 10 doses can be used from a single prepared investigational vaccine final product.

After mixing the investigational product, the combined final product can be held for up to 12 hours post preparation at 2 to 8 °C or at controlled room temperatures (up to 23 to 27 °C) and must be protected from light. Syringes containing the final product should be covered to limit exposure to light as well.

For all stages , the pharmacist will prepare a single dose for each subject based on study arm assignment.

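### Section 6.2.3 gives two in-use limits, 12 hours and 6 hours, that both reach the stage 4 BNT162b2 bivalent BA.4/BA.5 product

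*Protocol*

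**What the plan says.** Protocol Section 6.2.3 lists in-use times for prepared doses, one bullet per product family. Two adjacent bullets concern BNT162b2.

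- The second bullet names the bivalent products (wildtype with BA.1, or wildtype with BA.4/BA.5) and allows "up to 12 hours between 2 and 30°C (35 to 86°F) after vial is first punctured".
- The third bullet starts with BNT162b2 and its B.1.351 and B.1.1.529 versions and ends with "Omicron BA.1 and BA.4/BA.5: up to 6 hours at room temperature after 1st vial is punctured".

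The same section sends sites to the manual of procedures (MOP), with the words "refer to the MOP for storage conditions for vaccine candidates as well as storage of diluent", but states the in-use times itself.

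Section 6.1.1 describes the BA.4/BA.5 product as "BNT162b2 bivalent (wildtype and Omicron BA.4/BA.5 100mcg/mL for stage 4". Section 6.1.2 gives the stage 2 supply as "BNT162b2, BNT162b2 (B.1.351) and BNT162b2 (B1.1.529 Omicron) at 500 mcg/mL concentration for stage 2", to be diluted. For the stage 4 bivalent vials it says that "neither dilution nor mixing are needed for these formulations". Table 1 assigns the bivalent platform to arms 16 (BA.1 + wildtype) and 17 (BA.4/BA.5 + wildtype) only, with 100 subjects each.

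**The concern.** An in-use time tells the site pharmacist when a prepared dose may no longer be given. If two lines of one section set different times for the same vial, up to 30 sites can follow the protocol in good faith and treat the same dose differently: one gives it, and another discards it or reports a deviation.

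Section 10.1.9.4 counts any non-compliance with the protocol as a deviation, to be reported within five working days of its identification. Whether a deviation occurred would then depend on which bullet was read. Participants have a direct interest too, because the limit exists to protect product integrity.

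**Working it through.** No sample size, power or error rate is involved. The check sets the passages side by side.

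**1. Which products does each bullet cover?**

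| | Second bullet | Third bullet |
|---|---|---|
| Products named | Bivalent wildtype + BA.1; bivalent wildtype + BA.4/BA.5 | BNT162b2; B.1.351; B.1.1.529, followed by Omicron BA.1 and BA.4/BA.5 |
| Limit | 12 hours | 6 hours |
| Temperature | 2 to 30°C | Room temperature |
| Clock starts | First puncture of the vial | Puncture of the first vial |

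**2. Is there a separate BA.4/BA.5 product for the third bullet to mean?** No. Section 6.1.1 and Table 1 contain one BA.4/BA.5 product, the stage 4 bivalent of arm 17. No monovalent BA.4/BA.5 vaccine is described. The label in the third bullet therefore either refers to a product that the second bullet already covers, or names one that this trial does not use.

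**3. Could the two limits belong to two preparations of that product?** No. The stage 4 vials are used without dilution or mixing (Section 6.1.2), so no second stage 4 preparation exists to carry its own limit.

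**4. Do the temperature conditions separate the bullets?** No. Room temperature is not defined for BNT162b2; the assumption is that it lies within 2 to 30°C. The controlled room temperature that the protocol gives for the Sanofi product, up to 23 to 27°C, does. Both clocks start at puncture. At room temperature the conditions overlap, and the conflict is confined to doses held there.

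**5. Is the time given elsewhere in the protocol?** Section 6.1.2 repeats the limits for the mRNA-1273 products (8 hours) and the Sanofi products (12 hours), both in agreement with Section 6.2.3. It gives none for BNT162b2, so the two bullets are the protocol's only statement.

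**6. Size of the conflict.** 12 − 6 = 6 hours, a ratio of 12 / 6 = 2. A BA.4/BA.5 dose used more than 6 and up to 12 hours after puncture at room temperature meets one bullet and breaches the other.

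**7. Which arms?**
- Arm 17: 100 planned subjects, exposed to the ambiguity without doubt.
- Arm 16: 100 more, only if BA.1 in the third bullet means the bivalent. It can also be read as a label for the stage 2 B.1.1.529 product. The upper bound is 100 + 100 = 200.
- Arm 12 (stage 2, Omicron + wildtype): not exposed. It combines the separate 500 mcg/mL components, which the third bullet lists. The protocol uses the name BNT162b2 bivalent for the stage 4 product only.

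**The case against.** The strongest reply is that the third bullet carries a stray label and sets no rival limit. It never uses the word bivalent, its other entries are the stage 2 products, and a clock that starts with the first vial suits doses combined from more than one vial. That may be how the text arose. It remains an inference, and it does not help a pharmacist who finds BA.4/BA.5 named beside a 6-hour limit. Even on this reading the bullet needs correcting.

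A second reply is that Sections 6.1.2 and 6.2.4 send sites to the MOP for preparation and handling. The MOP is not among the documents reviewed and may settle the matter in practice, which lowers the expected impact. But Section 6.2.3 states the in-use times itself, and no single MOP value for the BA.4/BA.5 product could agree with both bullets.

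A third reply concerns scale, and it stands. Vaccine is prepared on the day it is given, one dose per subject, and nothing in the protocol says how many doses, if any, would be used in the disputed window.

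Two stronger readings are tempting and are not supported. A reader might infer that all 200 stage 4 subjects, and arm 12 as well, are affected; step 7 shows why not. A reader might also infer that subjects will drop out of the per-protocol set. Section 9.3 excludes data after a deviation only where that deviation is judged to affect the science, and Section 9.4.2 summarises immunogenicity on the mITT population with a per-protocol analysis as an option. That effect is conditional.

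**Conclusion.** The concern holds in limited form. Section 6.2.3 is inconsistent about the in-use time of the stage 4 bivalent BA.4/BA.5 product: 12 hours in one bullet, 6 hours in the next. Arm 17 (100 planned subjects) is clearly exposed to the ambiguity. Arm 16 is exposed on the broader reading only, and arm 12 is not. In practice it bears only on doses held at room temperature and given more than 6 and up to 12 hours after puncture, a number the protocol does not let one estimate.

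The conclusion rests on the protocol describing no other BA.4/BA.5 product and on room temperature lying within 2 to 30°C. Sample size and planned estimates are unaffected. It is nevertheless an operative handling instruction that bears on product integrity, so it should be corrected.

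**What to change.** Reconcile the two bullets. List each BNT162b2 presentation once, by stage (stage 2 diluted products, stage 4 ready-to-use bivalent products), with one in-use limit and one temperature condition each. Remove or correct the BA.1 and BA.4/BA.5 label in the 6-hour bullet as the sponsor and manufacturer confirm, and check that the MOP says the same. Which limit is right is for them to state; no view is given here.

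The cost is one or two corrected bullets and a check against the MOP. If stage 4 doses have already been given, sites need one clarification of which line applies, so that deviations are classified alike.

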6.2.4 Preparation

Refer to the protocol-specific MOP for details about preparation.

6.3 Measures to Minimize Bias: Randomization and Blinding

6.3.1 Treatment Assignment Procedures

Per International Council for Harmonisation of Technical Requirements for Pharmaceuticals for Human Use (ICH) guideline E6: GCP, screening records will be kept at the participating site to document the reason why an individual was screened, but failed trial entry criteria. The reasons why individuals failed screening will be recorded in Advantage eClinical, the electronic data capture (EDC) system that the Statistical and Data Coordinating Center (SDCC) develops and manages.

Once consented and upon entry of demographic data and confirmation of eligibility for this trial, the subjects will be enrolled.

6.3.2 Randomization and Blinding

Subjects will be randomized to study intervention in an equal allocation ratio for each stage. The study will be open label and study sites will administer product to a subject according to which study arm the subject has been assigned. Sites will be asked to recruit for all arms within a stage.

6.3.3 Blinding and Masking Procedures

This study is unblinded.

6.4 Study Intervention Compliance

Each dose of study product will be administered by a member of the clinical research team that is qualified and licensed to administer the study product. Administration and date, time, and location of injection will be recorded on the appropriate DCF.

6.5 Concomitant Therapy

Concomitant medications include prescription medications and vaccinations taken within 28 days of screening or Day 1. Topical, ophthalmic and otic medications, herbal supplements and vitamins will not be collected. This information is asked to assess eligibility. Only COVID-19 vaccination received at any time in the past will be captured in the trial database. After enrollment, immunosuppressant drugs, COVID-19 vaccines received outside of the study as well as COVID-19 related treatment and prophylaxis should be reported at any time during study participation and captured in the trial database. At each study visit, if there are new SAEs, concomitant medications should be recorded on the appropriate DCF and not included in the database unless these are immunosuppressant drugs, COVID-19 vaccines received outside of the study or COVID-19 related treatment and prophylaxis.

6.5.1 Rescue Medicine

Not Applicable.

6.5.2 Non-Research Standard of Care

Not Applicable.

7. STUDY INTERVENTION DISCONTINUATION AND SUBJECT DISCONTINUATION/WITHDRAWAL

7.1 Halting Criteria and Discontinuation of Study Intervention

7.1.1 Halting Criteria

The study will be halted in a given arm if any of the following events occur following any dose:

- 1- Any subject experiences an SAE after administration of the vaccine that is considered related to vaccine.
- 2- Any subject experiences laryngospasm, bronchospasm or anaphylaxis within 24 hours after administration of vaccine that is considered related to vaccine.
- 3- Any subject experiences ulceration, abscess or necrosis at the injection site that is considered related to vaccine administration.
- 4- Two (2) or more subjects experience an immediate IgE-mediated allergic reaction such as generalized urticaria (defined as occurring at three or more body parts) that is considered related to vaccine.
- 5- Three (3) or more subjects experience a Grade 3 AE (unsolicited) related to vaccine administration, in the same Preferred Terms based on the Medical Dictionary for Regulatory Activities (MedDRA) coding.
- 6- One (1) or more participant with myocarditis and/or pericarditis meeting the CDC case definition that is considered related to study vaccine.

7.1.2 Criteria for Continuation of Dosing and Redosing

In the event a halting rule is met:

An unscheduled safety analysis by the DSMB will be required for approval of further enrollment

Further administration of any study vaccine boost arms will be suspended until an assessment by the DSMB takes place.

7.1.3 Discontinuation of Study Intervention

For any arm of the study where participants will receive more than a single dose, subjects will need to be reassessed prior to the second dose. The following events constitute contraindications to any further administration of study vaccines. If any of these events occur during the study prior to the next vaccination, the subject will not receive the next vaccination but will be encouraged to continue study participation for safety and immunogenicity evaluations as per the Schedule of Activities for subjects receiving a single dose of vaccine.

- Any clinically significant medical condition that, in the opinion of the participating site PI or appropriate sub-investigator, poses an additional risk to the subject if he/she continues to participate in the study.
- Receipt of SARS-CoV-2 vaccine outside of the study or SARS-CoV-2 immunoglobulin, monoclonal antibody or plasma antibody.

- Confirmed symptomatic or asymptomatic SARS-CoV-2 infection after entry.
- Anaphylaxis or unexpected systemic hypersensitivity reaction following the administration of a prior study vaccination.
- Any SAE judged to be related to vaccine.
- Pregnancy.
- New information becomes available that makes further participation unsafe or interferes with the evaluation of responses.
- Termination of this trial.

7.1.3.1 Delay of Study Vaccination

If any of these events occur at the time scheduled for vaccination, the subject may be vaccinated at a later date.

- Acute moderate or severe infection with or without fever at the time of vaccination.
- Fever, defined as oral temperature $\geq 38.0^{\circ}\text{C}$ (100.4°F) at the time of vaccination.

Subjects with a minor illness without fever, as assessed by the participating site PI or appropriate sub-investigator, can be administered vaccines. Subjects with an oral temperature of 38.0°C (100.4°F) or higher will be re-contacted within the window specified in the SOA and re-evaluated.

For subjects for whom a second dose is planned, it is preferred that the vaccination still occur within the window specified in the SOA if possible but delays outside the windows are permitted (would still be a protocol deviation). If intercurrent SARS-CoV-2 infection occurs between the first and prior to the planned second study dose, no second vaccination will be given.

7.1.4 Follow-up for Subjects that Discontinued Study Intervention

Discontinuation of study intervention does not require discontinuation from the study, and the remaining study procedures should be completed. Participants who do not receive a second dose will revert to the schedule of activities (SOA) for single dose participants.

If a clinically significant finding is identified, including, but not limited to, changes from baseline, after enrollment, the participating site PI or qualified designee will determine if any change in subject management is needed ([Table 3](#)).

